Describe past experimental and/or clinical findings leading to the formulation of your study. For research involving unapproved drugs, describe animal and human studies. For research that involves approved drugs or devices, describe the FDA approved	Nursing students experience higher levels of stress than students in any other health science academic programs (Kinchen & Loerzel, 2019). Since most nursing students are not able to avoid these stressors, students must be able to cope with them. If students are not able to manage their stress, it can affect their performance, health, attitude, and role satisfaction as a nurse (Rafati et al., 2017). The levels of stress may vary during students' educational training, depending on their ability to adopt various strategies or coping with stress, and other factors. Even though numerous studies have been published regarding stress and anxiety among nursing students, few studies are found addressing the benefits of music utilized as an intervention to decrease emotional stress.

uses of this drug/device in relation to your protocol.
	

Item 4 Purpose and rationale Insert purpose, objectives and research questions/hypotheses here. If you cut and paste from another document, make sure the excerpted material answers the question
	
Music is an immensely powerful emotional tool that can be used as a coping mechanism for stress, but there is truly little existing research about its use by students. This study aims to explore the effects of music intervention on the stress and anxiety levels among nursing students in their first semester of undergraduate studies. Increased awareness of their own strategies used, as well as the willingness to use holistic methods such as music, can offer a non-pharmacological and inexpensive intervention to many institutions.
 
Research Questions:
 
 1. Is there a relationship between listening to music and stress, anxiety, and academic performance among new undergraduate nursing students? 2. Does listening to music help in decreasing anxiety among new undergraduate nursing students who are anticipating a skills assessment? 3. Does listening to music help in decreasing stress among new undergraduate nursing students who are anticipating a skills assessment? 4. Does listening to music help to improve academic performance among new undergraduate nursing students?

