The study will be conducted at the UT Health Science Center - San Antonio's Center for Simulation Innovation (CSI). Two classrooms will be reserved in the CSI area at the School of Nursing. Students will be divided into the recording time slots consisting of no more than 10 students at a time. The students receiving the music intervention will be assigned an iPad (only used to sync smartwatch), a hard copy of State Trait Anxiety Inventory (STAI) survey forms Y-1 and Y-2, a demographic data form, pencil, and smart watch. Students will be advised to sit quietly, with desks spread out, in the reserved room. The participants will be asked to complete the STAI survey forms prior to music listening. Students will be advised to wear the watch, and watches will be previously logged in and synced by researcher to measure heart rate and blood pressure. Vital sign sheet will be completed by researcher using the data from the iPad. Fifteen minutes of classical music will be played overhead in the classroom. The students will be instructed not to use other electronic devices such as ear buds or phones during this time. The STAI survey Y-1 will be completed again post-intervention, and heart rate and blood pressure re-assessed. Students will then proceed to perform the skills competency assessment. Vitals and STAI survey Y-1 will then be reassessed post-skills competency and academic performance (pass/fail) will be measured.

The students who will not be receiving the music intervention (control group) will be seated in a second reserved classroom and will be repeating the same process as the music intervention group except without music, instead they will be sitting quietly for 15 minutes waiting to record their skills competency. The students will also be instructed not to use other electronic devices such as ear buds or phones during this time. For any students who have been randomly assigned to either group, and refuse to be in the study, they

will be allowed to leave. Only the academic performance will be measured on these students that refuse to be assigned to a group.

Data Analysis Plan:

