A priori power analysis was conducted using G*Power 3.1.9 to determine the minimum sample size required to find statistical significance using a 3 (group) x 4 (time) repeated measures analysis of variance (i.e., a mixed-model ANOVA). With a desired level of power set at .80, an alpha (α) level at .05, and a moderate effect size of .25 (f), it was determined that a minimum of 30 total participants would be required to ensure adequate power (Cohen, 1988).

Mean heart rate, mean blood pressure, mean scores on STAI, and academic performance score (Pass/Fail) will be calculated for all groups. Demographic data will be analyzed in terms of frequencies and comparisons between groups. For RQ1: Pearson's correlation will examine the relationship between the music intervention on stress, anxiety, and academic performance. For RQ2: To measure anxiety, STAI mean scores will be analyzed. For RQ3: To measure stress levels, the mean heart rate and mean blood pressure will be analyzed. For RQ4: To assess academic performance, Pass/fail scores will be looked at. MANOVA will be considered for data analysis since there is one independent variable (music intervention) and multiple dependent variables. If any variables are not correlated, running a repeated-measures ANOVA to detect any overall differences between any related means would be considered. A paired samples t-tests could also be used for pre-and post-comparisons of vital signs. Using a Chi-Square test can also be beneficial in determining any differences in demographics and anxiety and/or stress. Alpha will be set at 0.05 for the study.

Item 7 Risks Section:

Complete the following table to describe the risks of all **research procedures** listed in Step 2, Institutional Form (items 28-34). *Do not list risks of Routine care procedures here.*

N/A, Risks are described in the informed consent document – do not complete this table.

Research procedures	Risks

example:
 
 • History and physical • Questionnaire • Laboratory tests 	
List the reasonably expected risks under the following categories as appropriate:

Add or delete rows as needed	
Vitals Signs obtained via SmartWatch	
Serious and likely;
 
 ○ None 
Serious and less likely;
 
 ○ None
Heart Rate Blood Pressure	
Demographic data form, paper and pencil	
Serious and likely;
 
 ○ None

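### RQ2 does not name the STAI form that answers it, and the analysis plan does not use the pre-music Y-1 and Y-2 scores as covariates, although both are already collected

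*Combined protocol and SAP*

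**What the plan says.** RQ2 in Item 4 asks: "Does listening to music help in decreasing anxiety among new undergraduate nursing students who are anticipating a skills assessment". That is a question about change under anticipation.

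Under Item 6, Step-by-Step Methods, each student in the music arm receives "a hard copy of State Trait Anxiety Inventory (STAI) survey forms Y-1 and Y-2", and "The participants will be asked to complete the STAI survey forms prior to music listening". After that only one form returns: "The STAI survey Y-1 will be completed again post-intervention", and later "Vitals and STAI survey Y-1 will then be reassessed post-skills competency". The control arm follows the same sequence without music. Y-1 therefore has three values per student and Y-2 has one, taken before the intervention.

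The Data Analysis Plan in Item 6 does not carry this distinction over. It states "Mean heart rate, mean blood pressure, mean scores on STAI, and academic performance score (Pass/Fail) will be calculated for all groups" and, for the anxiety question, "For RQ2: To measure anxiety, STAI mean scores will be analyzed". MANOVA is to be considered, with the music intervention as the single independent variable, and repeated-measures ANOVA is the fallback if variables prove uncorrelated. Paired t-tests are mentioned for vital signs only. No covariate appears, and Y-2 is given no role.

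**The concern.** A Y-2 score recorded before music cannot be changed by music. It is a baseline measure, whatever use is made of it. An outcome described only as the STAI mean leaves three poor analyses open:

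- averaging the two forms, which mixes a score that can respond with one that cannot;
- setting a two-form baseline against a one-form follow-up, which are not the same measure;
- entering Y-2 among the MANOVA's unlisted dependent variables, or in the RQ1 correlation. An arm difference there would reflect only how the arms differed before music, whether by chance or through selective refusal, since students may withdraw after assignment.

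The second issue does not depend on how the wording is read. The trial collects two pre-music anxiety scores, and the analysis plan uses neither to reduce the noise in the arm comparison.

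**Working it through.** **The plan's own figure.** The only number in the analysis plan is the minimum of 30 participants for a 3 (group) × 4 (time) mixed ANOVA with f = .25, alpha .05 and power .80. For the group-by-time interaction, assuming a correlation of .5 between repeated measures and sphericity (neither is stated), λ = f²·N·m/(1−ρ) = .0625 × 30 × 4/.5 = 15, with (3−1)(4−1) = 6 and (30−3)(4−1) = 81 degrees of freedom. Power is 0.809, so 30 reproduces. It does not show which STAI form was meant, because four time points match neither form's schedule.

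**If the forms were averaged.** Assume equal SDs, state-trait correlation r and no effect on Y-2. The raw difference is multiplied by 0.5 and the SD by √((1+r)/2), so the standardised effect is multiplied by 0.5/√((1+r)/2). The sample size for equal power is multiplied by the inverse square, 2(1+r).

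| r | effect kept | sample-size multiplier |
|---|---|---|
| .4 | .598 | 2.8 |
| .5 | .577 | 3.0 |
| .6 | .559 | 3.2 |

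For illustration, take a true Y-1 effect of d = 0.5 and 54 students per arm (the Phase 2 cohort of about 108 split equally), with clustering ignored. Power is 0.73 on post-music Y-1 alone. On the averaged score it is 0.36 to 0.27 for r = .3 to .8. If Y-2 is kept out of the outcome, or analysed as a separate variable, the loss in the Y-1 comparison is zero.

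**Adjusting for baseline Y-1.** With baseline-post correlation r₁, adjustment leaves a fraction 1 − r₁² of the outcome variance: .64 at r₁ = .6 and .51 at r₁ = .7. It therefore removes 36% to 49%. In the same illustration the effective d becomes 0.5/√.64 = 0.625 or 0.5/√.51 = 0.70, and power rises from 0.73 to 0.90 or 0.95.

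A repeated-measures ANOVA with baseline as a time level already uses baseline Y-1 in another way. Its pre-to-post interaction contrast is a comparison of change scores, with variance 2(1 − r₁) = .80 or .60. Against that, adjustment has relative variance .64/.80 = .80 or .51/.60 = .85, so the gain is 20% to 15%.

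**Adding Y-2.** With trait-post correlation r₂ = .5 and trait-baseline correlation r₁₂, R² = (r₁² + r₂² − 2r₁r₂r₁₂)/(1 − r₁₂²).

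| r₁ | r₁₂ | R², baseline Y-1 only | R², both | further residual variance removed |
|---|---|---|---|---|
| .6 | .5 | .36 | .413 | 1 − .587/.64 = 8.3% |
| .6 | .6 | .36 | .391 | 1 − .609/.64 = 4.8% |
| .7 | .5 | .49 | .520 | 1 − .480/.51 = 5.9% |
| .7 | .6 | .49 | .500 | 1 − .500/.51 = 2.0% |

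Most of the precision comes from baseline Y-1, and Y-2 adds a little. The documents give no SD, correlation or expected STAI effect, so all of these inputs are assumptions.

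**The case against.** A reader might infer that Y-2 enters the RQ2 outcome means as the plan stands, and that the anxiety result is therefore diluted about threefold in sample-size terms. The documents do not support this. Nowhere is Y-2 called an outcome, averaged with Y-1, or set in a two-form baseline against a one-form follow-up. The methods name the forms separately and repeat only Y-1, RQ2 asks about a decrease, and a repeated-measures ANOVA needs a repeated score, which among the STAI forms only Y-1 provides. A Y-1-only reading is the natural one, and under it the dilution is nil. On this view, failing to name the form is missing detail.

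It can also be said that covariate use is not the only proper role for Y-2, since describing baseline comparability is equally legitimate, and that a 2% to 8% gain is small. Both points are fair. They do not answer the adjustment point: the listed methods include no covariate, and adjusting for baseline Y-1 is a concrete improvement on an unadjusted MANOVA and, under the assumed correlations, on a change-score contrast.

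**Conclusion.** The point holds as a low-cost improvement together with a clarification; it does not show that the planned anxiety analysis is invalid. RQ2 lacks a named form, time point and contrast, and the plan makes no covariate use of the pre-music scores.

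The drop to 56% to 60% of the effect is conditional on averaging the forms, so the honest range runs from no loss up to that. The benefit of adjustment rests on assumed correlations: 36% to 49% of variance against an unadjusted post-music comparison, 15% to 20% against a change-score contrast, and a further 2% to 8% of residual variance from Y-2.

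One limit applies. Both forms are completed before music but after students are seated in their arm's room, so they are baseline values only to the extent that knowing the allocation does not alter the answers.

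**What to change.** Replace the RQ2 sentence in the Data Analysis Plan of Item 6 with:

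> RQ2 is answered by comparing arms on post-music STAI Y-1 (state), adjusted for baseline Y-1 and for Y-2 (trait) as baseline covariates. Post-skills Y-1 is analysed in the same way as a secondary time point. Y-2 is not an outcome and is not combined with Y-1; the same applies to the STAI term in RQ1 and in any MANOVA.

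Baseline Y-1 must be named explicitly, because the small extra gain from Y-2 presumes that it is in the model.

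The cost is a few sentences and two degrees of freedom. With 108 students in two arms, and clustering ignored, residual degrees of freedom go from 106 to 104; with the pilot's maximum of 20 they go from 18 to 16. No further data collection is needed. Making the change before the data are examined also removes any choice of form or time point after the results are known.

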COVER PAGE FOR PROTOCOL AND STATISTICAL ANALYSIS PLAN

Official Study Title: The Effects of a Music Intervention on Stress, Anxiety and Academic Performance on Nursing Students

NCT number: NCT05590910

IRB Approval Date: 05.23.2022

Unique Protocol ID: HSC20210672H

Protocol Template Form

Item 1 UTHSCSA Tracking Number	HSC20210672H: The Effects of a Music Intervention on Stress, Anxiety and Academic Performance on Nursing Students
---------------------------------------	--

Item 2 Abstract / Project Summary	Provide a succinct and accurate description of the proposed research. State the purpose/aims. Describe concisely the research design and methods for achieving the stated goals. This section should be understandable to all members of the IRB, scientific and non-scientific. DO NOT EXCEED THE SPACE PROVIDED.
--	--

Purpose/Objectives: The purpose of this study is to assess whether a music intervention, compared with no music intervention, influences stress and anxiety levels and academic performance of undergraduate nursing students.

Research Design/Plan: A randomized controlled approach will explore the effects music has on stress and anxiety levels and academic performance among undergraduate nursing students.

Methods: Students will be divided and randomized into two recording groups: 1.) Music Intervention Group, 2.) Non-Music Control Group. The music intervention group will receive a 15-minute music intervention and variables such as heart rate, blood pressure, anxiety, and academic performance will be measured. The non-music control group will not receive the intervention; however, the same variables will be measured.

Clinical Relevance: Music has been shown to beneficially affect stress-related physiological, as well as cognitive, and emotional processes. The proposed study has the potential to highlight the acceptance of music used as a strategy for impacting stress and anxiety experienced by nursing students during their undergraduate studies. Evidence of any effect music has on stress and anxiety levels among undergraduate studies can determine existence by the measurement of vital signs, STAI responses, and skills performance. This type of study can be beneficial to further research and can be implemented by nurse educators, healthcare institutions, and wellness clinics.

Item 3 Background	

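### RQ2 and RQ3 have no committed between-arm test, time point or baseline adjustment; a baseline-adjusted arm comparison at the pre-skills assessment would use data already planned

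*Combined protocol and SAP*

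**What the plan says.** All references are to the combined protocol and SAP.

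- **Objective (Item 2, Purpose/Objectives).** The study is to assess "whether a music intervention, compared with no music intervention, influences stress and anxiety levels and academic performance of undergraduate nursing students". This is a between-arm question. RQ2 and RQ3 (Item 4) narrow it to anxiety and stress in students who are anticipating a skills assessment.
- **Measurements (Item 6, Step-by-Step Methods).** The state-anxiety form (STAI Y-1) is completed before the 15 minutes, after them, and again after the skills assessment. Heart rate and blood pressure are re-assessed at the two later points; a baseline reading is implied by that wording and by the pre-synced watches. Controls go through the same process, sitting quietly for 15 minutes in place of music.
- **RQ2 and RQ3 (Item 6, Data Analysis Plan).** The anxiety sentence reads "For RQ2: To measure anxiety, STAI mean scores will be analyzed", and the stress sentence reads "For RQ3: To measure stress levels, the mean heart rate and mean blood pressure will be analyzed". Neither gives a test, contrast or time point.
- **Other analyses in the same section.** RQ1 is given a Pearson analysis, in which "correlation will examine the relationship between the music intervention on stress, anxiety, and academic performance". A multivariate option follows: "MANOVA will be considered for data analysis since there is one independent variable (music intervention) and multiple dependent variables". The next option is conditional and equally tentative: "If any variables are not correlated, running a repeated-measures ANOVA to detect any overall differences between any related means would be considered". The last of these options is a within-person test: "A paired samples t-tests could also be used for pre-and post-comparisons of vital signs". The power paragraph rests on a three-group, four-time "repeated measures analysis of variance (i.e., a mixed-model ANOVA", but no research question is assigned that model.

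**The concern.** The analyses left open answer different questions. A MANOVA or a correlation with arm compares the arms. A paired t-test asks whether one group changed over time. The repeated-measures ANOVA sentence speaks of related means and does not say whether an arm term is included. With no choice fixed for RQ2 or RQ3, it can be made after the data are seen.

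Two things are at stake. First, the design collects a baseline for each outcome, but no listed analysis is said to use it for adjustment, so precision may be lost for nothing. Second, for RQ3 a significant pre-post change in heart rate or blood pressure in the music arm could be taken as a music effect, although 15 minutes of quiet sitting or growing anticipation might produce the same change in both arms.

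**Working it through.** **Which assessment answers the question.** Of the three, only the second falls after the intervention and before the skills assessment. It is the one that matches RQ2 and RQ3.

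**The plan's own figure.** Inputs from the power paragraph: 3 groups, 4 times, f = .25, alpha .05, power .80. The within-person correlation is not given; r = .5 with sphericity is assumed.
- Group x time interaction: noncentrality = f² × N × 4/(1 − r), with 6 and 3(N − 3) degrees of freedom.
- N = 30: .0625 × 30 × 4/.5 = 15.0, df 6 and 81, power .809.
- N = 27: noncentrality 13.5, power .754.

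So the stated 30 reproduces as the omnibus interaction of a 3 x 4 layout. The trial has two arms (Item 2) and three assessments of these outcomes (Item 6).

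**Power of an arm comparison at the pre-skills assessment.** Assumptions: music effect 0.5 SD, two-sided alpha .05 (the plan does not state sidedness), independent students, and 54 per arm (half of the roughly 108 in Phase 2). The noncentrality is 0.5/√(2v/n), where v is the variance factor:
- post-only: v = 1, df 2n − 2
- ANCOVA: v = 1 − r², df 2n − 3
- change score from baseline: v = 2(1 − r), df 2n − 2

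For example, at r = .5 ANCOVA has 0.5/√(2 × .75/54) = 3.00, and post-only has 0.5/√(2/54) = 2.60.

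| Baseline correlation r | Post-only | ANCOVA | Change score |
|---|---|---|---|
| 0 | .73 | .73 | .44 |
| .3 | .73 | .77 | .59 |
| .5 | .73 | .84 | .73 |
| .7 | .73 | .95 | .91 |

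The pre-skills contrast taken from a group x time model is the change-score column. It equals post-only at r = .5, because 2(1 − .5) = 1, and is worse below that.

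**The model nearest the power paragraph, in the actual layout.** This is a 2 x 3 omnibus interaction with 54 per arm and r = .5. Let the arm differences at the three assessments be (0, .5, 0) if the effect fades or (0, .5, .5) if it persists. The squared deviations from their mean sum to .1667 in both cases. Noncentrality = 108 × (.1667/4)/(1 − .5) = 9.0, df 2 and 212, power about .76.

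**ANCOVA at the stated minimum.** With 15 per arm and r = .5, noncentrality is 1.58, df 27, power .33. Reaching .80 takes 49 per arm, or 98 in total.

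**Paired t-test in the music arm when music does nothing.** Assume a change of 0.3 SD shared by both arms. The standardised change is 0.3/√(2(1 − r)) = .212, .300 and .387 at r = 0, .5 and .7. With n = 54 the test is significant in 33%, 58% and 80% of trials. These are correct detections of change over time, not errors in themselves.

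**The case against.** **The plan already contains between-arm analyses.** This is true, so a reader should not infer that the arms will go uncompared. A Pearson correlation of a two-arm indicator with an outcome gives the same p-value as the two-sample t-test, and the RQ1 sentence commits to it. MANOVA has music as its independent variable, and the power paragraph assumes a group term. But the correlation belongs to RQ1 and has no time point, MANOVA is only to be considered, and the mixed model appears only in the sample-size calculation.

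**The research questions already imply the time point.** The reference to students anticipating an assessment does point to the second measurement. The analysis section never says so.

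**The paired test is optional.** This stands. A reader might infer that the plan will present a pre-post change as a music effect. It does not say that; it merely leaves the test unlabelled. The permission covers vital signs only, so this part does not extend to RQ2.

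**The power loss could be overstated.** This also stands. One might suppose that outcomes will be averaged over several assessments, with a much larger loss, but no section proposes that. Against the 2 x 3 omnibus interaction, the ANCOVA advantage at r = .5 is .84 against about .76.

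**A group x time interaction would serve equally well.** It would not, as the table shows. Nor does a single pre-skills contrast match the power paragraph, which concerns an omnibus test in a different layout.

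**Conclusion.** The concern holds in this form: for RQ2 and RQ3 the plan fixes no test, no time point and no baseline adjustment, and for RQ3 it also permits a paired test that cannot separate music from a change shared by both arms. It should be fixed before outcome data are examined.

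The gain from ANCOVA over an unadjusted comparison with 54 per arm is nil at r = 0, about .04 at r = .3, .11 at r = .5 and .22 at r = .7. It rests on an assumed 0.5 SD effect, assumed correlations and independent students; the documents give none of these for this comparison. The paired-test percentages rest on an assumed 0.3 SD shared change and matter only if the result is read as an effect of music.

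The documents do not support reading this as an absence of any between-arm analysis, or as a plan to claim music effects from within-arm change. Session effects are a separate matter. Phase 1 has one sign-up group per arm, so no analysis there can separate music from session. For Phase 2, Item 6 does not settle whether whole sessions are assigned to arms.

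**What to change.** In the Data Analysis Plan, state the following:

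1. For RQ2 and RQ3, the test of music is the between-arm difference at the post-intervention, pre-skills assessment, by ANCOVA: STAI Y-1 adjusted for baseline Y-1, and heart rate and blood pressure each adjusted for their own baseline.
2. If Phase 2 assigns whole sessions to arms, the analysis accounts for session.
3. The post-skills assessment is secondary.
4. Paired t-tests and time effects are descriptive and are not evidence about music. The group x time change-score contrast is not to be offered as equivalent to ANCOVA.
5. Phase 1 is for feasibility and variance estimation.

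State explicitly that vital signs are recorded at baseline, since this is now only implied.

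The cost is analysis wording, with no new measurements, plus a restated power calculation. The minimum of 30 belongs to the 3 x 4 interaction. For this ANCOVA, with a 0.5 SD effect and r = .5, power is about .33 with 30 students and .84 with 108, before any allowance for session effects or for students who remove themselves. Which outcome is primary, and how several outcomes are handled, needs its own statement.

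### If the joint MANOVA named first in the plan is used, one failed watch reading also discards that student's valid STAI; a mixed model per outcome would keep it

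*Combined protocol and SAP*

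**What the plan says.** Item 6 (Step-by-Step Methods) has each student complete STAI Y-1 and have heart rate and blood pressure read from a watch on three occasions: before the 15 minutes of music or quiet sitting, after it, and after the skills test. Of the third occasion it says: "Vitals and STAI survey Y-1 will then be reassessed post-skills competency". Students who decline may leave, and of them it says: "Only the academic performance will be measured on these students that refuse to be assigned to a group".

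Item 6 (Data Analysis Plan) then says: "MANOVA will be considered for data analysis since there is one independent variable (music intervention) and multiple dependent variables". Repeated-measures ANOVA is a second possibility if variables turn out to be uncorrelated. Paired t-tests are a further option for vital signs. STAI (RQ2), vital signs (RQ3) and pass/fail (RQ4) are listed as separate questions, and pass/fail is to be summarised for all groups. On sample size the plan states that "a minimum of 30 total participants would be required to ensure adequate power".

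The document does not say which outcomes and occasions would enter a MANOVA or how a missing reading or form is handled. It defines no analysis set and adds no allowance for loss to the 30.

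**The concern.** MANOVA works on complete rows. If the dependent variables are the three outcomes at three occasions, a student with one blank cell leaves the whole analysis. A watch that fails once then costs the student's STAI record, which does not depend on the watch.

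Classical repeated-measures ANOVA has a milder form of the same problem. Run on STAI alone, it ignores watch failures, but it needs all three STAI forms. RQ2 and RQ3 in Item 4 ask about students who are still awaiting the skills test, so the readings that answer them are taken before the test. Dropping a student because the form after the test is missing throws away the readings that the question needs.

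Two things are at stake: precision, chiefly if the numbers are near the stated minimum or in the pilot, and some bias if the students lost after the test were the more anxious ones before it.

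**Working it through.** **The plan's own figure.** Inputs from Item 6: 3 groups (k), 4 times (m), f = 0.25, alpha 0.05, power 0.80. Assumed, because not stated: correlation 0.5 between occasions, and sphericity. For the group-by-time interaction:

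- λ = f²·N·m/(1 − ρ) = 0.0625 × 30 × 4/0.5 = 15
- df1 = (k − 1)(m − 1) = 6; df2 = (N − k)(m − 1) = 81
- power = 0.809, so N = 30 reproduces, with nothing added for loss.

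**How many students a complete-row rule removes.** With loss probability p per event and c events that must all be present, the share lost is 1 − (1 − p)^c. The rates p are assumptions, with events taken as independent.

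- c = 3: one outcome over three occasions
- c = 6: one watch event (heart rate and blood pressure together) and one form on each of three occasions
- c = 9: heart rate, blood pressure and STAI all failing independently

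| p | c = 3 | c = 6 | c = 9 |
|---|---|---|---|
| 1% | 3.0% | 5.9% | 8.6% |
| 2% | 5.9% | 11.4% | 16.6% |
| 5% | 14.3% | 26.5% | 37.0% |

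Of the roughly 108 students in Phase 2, c = 3 leaves about 105, 102 or 93; c = 6 leaves about 102, 96 or 79; c = 9 leaves about 99, 90 or 68. Six events is the more realistic count, because both vital signs come from the same watch at the same moment. Of 30 students, c = 6 leaves about 28.2, 26.6 or 22.1.

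**What the loss costs in power.**

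- By the plan's own 3 x 4 criterion, starting from 30, power falls from 0.81 to 0.77 with 28 complete students, 0.73 with 26 and 0.64 with 22.
- With two arms and three occasions, interaction power is still 0.999 with 80 complete students and 0.996 with 68, so at cohort size that test barely suffers.
- For a single between-arm comparison after the wait, with d = 2f = 0.5, equal arms and no adjustment, power is 0.73 at 108, 0.59 at 79 and 0.53 at 68.

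All of these ignore clustering by sign-up group.

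**Which records go.** In a simulated cohort of 108, one student had a failed heart-rate reading, a second had no post-skills STAI form, and 10 refusers had pass/fail only.

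- Joint MANOVA with pass/fail included: 108 − 1 − 1 − 10 = 96 kept. The first student's STAI is lost.
- Repeated-measures ANOVA on STAI: 108 − 1 − 10 = 97 kept. The first student stays; the second loses two valid earlier scores.
- Pass/fail compared by group: all 108 kept.

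**Bias from selective loss.** Let the pre-skills score x be N(0, 1) in controls and N(−0.5, 1) with music, and let the probability of a missing post-skills reading be 1/(1 + exp(−(a + b·x))), with a set to give the overall missing rate. Slopes b of 1.0 and 1.5 multiply the odds of missing by 2.7 and 4.5 per SD, which is steep. After those students are deleted, the true difference of 0.50 SD becomes:

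- at 5% missing: 0.480 (b = 1.0) or 0.464 (b = 1.5)
- at 10% missing: 0.466 or 0.441
- at 20% missing: 0.445 or 0.409

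With b = 0.5 and 5% missing it is 0.494.

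**The case against.** The strongest reply is that the plan commits to none of this. MANOVA and repeated-measures ANOVA are only under consideration, the research questions take STAI and vital signs one at a time, and no sentence puts all outcomes and occasions into one MANOVA. That stands, and it makes the loss conditional. It does not remove the point: MANOVA is the method named first for comparing the groups, its stated reason is that there are several outcomes, and repeated-measures ANOVA also drops partial records. The paired t-tests do keep a pre/post pair when only the post-skills reading is missing, but they are offered for vital signs only and do not compare the arms.

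A reader might infer two stronger things that the documents do not support. One is that either method removes STAI when a watch fails; this happens only in the joint MANOVA. The other is that every refuser's pass/fail result disappears. It would be lost only if pass/fail were entered in the MANOVA, and nothing says it would be. Pass/fail is measured once, has its own question and is summarised for all groups.

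It is also fair to object that the missing rates and slopes are invented, and that heavy loss is unlikely when all three assessments are supervised around one required skills recording. For that reason the results are shown as ranges, and the low end is modest.

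**Conclusion.** The point holds as a conditional risk with a cheap remedy. If the joint MANOVA is used, any one missing value removes the whole student. Under assumed loss of 1% to 5% per event this is about 6% to 26% of students (9% to 37% if all nine values fail independently), against 3% to 14% for one outcome analysed alone. Repeated-measures ANOVA per outcome avoids the loss across outcomes, but still discards valid pre-skills readings when a later one is missing.

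At about 108 students the cost depends on the test: negligible for the interaction, but visible for the single post-wait contrast at the upper end of the assumed range. It matters more near 30 students. Bias is possible but small at low missing rates: 0.50 SD becomes about 0.46 to 0.48 at 5% missing, even under steep slopes. Every missing rate here is an assumption.

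**What to change.** In Item 6 (Data Analysis Plan), replace MANOVA and repeated-measures ANOVA with a separate likelihood-based mixed model for each of STAI Y-1, heart rate and blood pressure. Include arm, time, arm-by-time and a student random effect, plus a random effect for the sign-up group or time slot where that is the unit randomised. Use every available reading, apply a small-sample degrees-of-freedom correction, and take the arm contrast at the assessment after the 15-minute wait. State that complete data across outcomes are not required. Compare pass/fail on its own by assigned group, including refusers whose assignment is known.

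The cost is plan wording and a standard routine, with no new data. There are three limits. The degrees of freedom are approximate in small samples. In the pilot, with at most 20 students in two sign-up groups, a group effect cannot be separated from arm by any model. The mixed model also recovers no STAI or vital signs for refusers, who supply none, and it relies on loss being explained by the readings that were observed.
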